8.5.1 Prohibited Treatment

During Screening and Induction Therapy, subjects are not permitted to receive rescue therapy for UC including increases in corticosteroids or other medications for UC treatment, except as specified above (Section 8.5).

During Screening, Induction Therapy, and OLE/LTE Therapy, subjects are not permitted to receive any additional experimental therapy or any other therapy to treat the UC, except as specified above. The following is a list of specific prohibited treatments:

- B-cell depleting agents including vedolizumab, natalizumab, efalizumab or rituximab or other lymphocyte-depleting treatments, including but not limited to alkylating agents (such as cyclophosphamide or chlorambucil) and total lymphoid irradiation;
- Methotrexate, cyclosporine, mycophenolate, tacrolimus, thalidomide, or other immune altering drugs; (*Note: ophthalmologic preparations are permitted.*)
- TNF antagonists.

The above prohibited treatments are permitted during the Induction Therapy Follow-up Period and OLE/LTE Therapy Follow-up Period of the study.

Some medications, such as nonsteroidal anti-inflammatory drugs, may need to be administered or held prior to a sigmoidoscopy with biopsy. Those will be detailed in a sigmoidoscopy manual.

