12 STATISTICAL METHODS AND PLANNED ANALYSIS

12.1 General Statistical Considerations

All categorical variables will be summarized by counts and percentages. Descriptive statistics (mean, standard deviation [SD], median, minimum, and maximum) for continuous variables will be utilized. All summaries and analyses conducted will be by treatment cohort (KHK4083 dose levels; combined KHK4083; and placebo) and by visit. The specifics for these outputs will be described in detail within the Statistical Analysis Plan (SAP). The last pre-administration observation will be used as the Baseline value for calculating post-administration changes from Baseline. For efficacy assessments, Baseline is defined as Week 0. Data obtained and entered into the database will be provided in separate data listings showing individual subject values. The planning and reporting of statistical analysis will be carried out as described in the Sponsor's work instructions and standard operating procedures (SOPs) governing clinical studies.

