Induction Therapy: Week 0 to Week 12 (Last Dose at Week 10)	
Double-blind Induction Therapy is separated into Part A for administration of multiple ascending IV doses of KHK4083 (or placebo) to subjects in Cohorts 1 - 3 and Part B for administration of the recommended IV dose (one of three dose levels identified in Part A) of KHK4083 (or placebo) to subjects in Cohort 4. Subjects in Part A are prohibited from participating in Part B.
	
Double-blind Induction Therapy is separated into Part A for administration of multiple ascending IV doses of KHK4083 (or placebo) to subjects in Cohorts 1 - 3 and Part B for administration of the recommended IV dose (one of three dose levels identified in Part A) of KHK4083 (or placebo) to subjects in Cohort 4. Subjects in Part A are prohibited from participating in Part B.

Forms

Title Statistical Analysis Plan Template

Code	Version	Effective Date	Page
FRM_ST03_032	01	23 Apr 2015	12 of 53

	Protocol Amendment 1	Protocol Amendment 2

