OLE Therapy Period								
OLE Therapy Period and OLE Therapy Follow-up Period								

1) Double-Blind Therapy Period includes both Double-Blind Induction Therapy Period and LTE Therapy Period.

2) Double-Blind Therapy Follow-up Period includes both Follow-up Periods after Double-Blind Therapy Period and LTE Therapy Period.

3) For subjects randomized to Placebo, they receive 4083 administration during the duration but they are summarized as one category as "Placebo".

Image which shows the relationship between summary pattern and data will be displayed in Figure 4.

Figure 4 Summary Patterns

Forms

Title Statistical Analysis Plan Template

Code

Version

Effective Date

[figure not shown]
Page

FRM_ST03_032

01

23 Apr 2015

21 of 53

General reporting conventions will include the following:

- The baseline value for any measurement is the last value obtained prior to receiving administration of KHK4083 or placebo on Day 1 at Week 0. All nominal time points will be used for analysis; actual assessment times will not be used to reclassify the time point at which a measure was taken.

	Forms			
	Title	Statistical Analysis Plan Template		
	Code	Version	Effective Date	Page
	FRM_ST03_032	01	23 Apr 2015	22 of 53

- Study day: Study day will be calculated relative to the date of KHK4083 or placebo administration (Day 1) as:
 - (If Date of event \geq Date of first investigational product administration) Date of event – Date of first investigational product administration + 1 and
 - (If Date of event $<$ Date of first investigational product administration) Date of event – Date of first investigational product administration

This formula will be used when calculating days to a specific event (i.e., concomitant medication and/or AE start date). A negative study day indicates an event prior to investigational product administration.

- Unless otherwise noted, all percentages will be presented to one decimal place.
- Individual data listings of all data represented on the eCRF will be provided as an appendix to facilitate investigation of the tabulated values and to allow for the clinical review of all variables. All data listings will be sorted by dose Cohort, site-subject number, visit, and time points where appropriate.
- Post-dose data from unscheduled visits will be excluded from the summary tables but included in the data listings.

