 - Glucocorticoid-free clinical remission at Week 52 will be defined in the case that clinical remission is present at Week 52 and no glucocorticoid listed in Section 9.3 is used from Week 16 through Week 52.
- Glucocorticoid dosages:
 - Baseline glucocorticoid dosages (times) will be defined as the total number of administrations of glucocorticoid listed in Section 9.3 that is used during Double-Blind Induction Period (from Day 1 to a day before Week 16). For the subject who receives no glucocorticoid, the dosages will be 0.

	Forms			
	Title	Statistical Analysis Plan Template		
	Code	Version	Effective Date	Page
	FRM_ST03_032	01	23 Apr 2015	32 of 53

- Glucocorticoid dosages (times) at Week 16 through Week 52 will be defined as the total number of administrations of glucocorticoid listed in Section 9.3 that is used during OLE/LTE Therapy Period (from Week 16 to Week 52). For the subject who receive no glucocorticoid, the dosages will be 0.
- Glucocorticoid dosages (times) at Week 16 through LTE Therapy Follow-up Period will be defined as the total number of administrations of glucocorticoid listed in Section 9.3 that is used during LTE Therapy Period and LTE Therapy Follow-up Period (from Week 16 to Follow-up 3). For the subject who receives no glucocorticoid, the dosages will be 0.
- Glucocorticoid dosages (times) at Week 16 through OLE Therapy Follow-up Period will be defined as the total number of administrations of glucocorticoid listed in Section 9.3 that is used during OLE Therapy Period and OLE Therapy Follow-up Period (from Week 16 to Follow-up 3). For the subject who receives no glucocorticoid, the dosages will be 0.
- If there is glucocorticoid that the number of administrations is unknown, it will be assumed that the glucocorticoid was used at a frequency of an administration per day.
- For the subjects who do not move to OLE/LTE Therapy Period, “Glucocorticoid dosages (times) at Week 16 through Week 52” and “Glucocorticoid dosages (times) at Week 16 through OLE/LTE Therapy Follow-up Period” will not be defined.
- Change from baseline in corticosteroid (glucocorticoid) dosages will be defined as follows:
 - Change from baseline in corticosteroid (glucocorticoid) dosages at Week 16 through Week 52 = Glucocorticoid dosages at Week 16 through Week 52 - Baseline glucocorticoid dosages

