 - Change from baseline in corticosteroid (glucocorticoid) dosages at Week 16 through LTE Therapy Follow-up Period = Glucocorticoid dosages at Week 16 through LTE Therapy Follow-up Period - Baseline glucocorticoid dosages
 - Change from baseline in corticosteroid (glucocorticoid) dosages at Week 16 through OLE Therapy Follow-up Period = Glucocorticoid dosages at Week 16 through OLE Therapy Follow-up Period - Baseline glucocorticoid dosages
- Duration of glucocorticoid-free treatment will be defined as the duration that no glucocorticoid listed in Section 9.3 is used from Week 16 through Follow-up 3.
 - Duration of glucocorticoid-free treatment (days) = Date of first glucocorticoid after Week 16 visit - Date of Week 16 visit
 - If the subject received glucocorticoid on the date of Week 16 visit, the duration of glucocorticoid-free treatment for the subject is 0.

A comparison between treatments (each KHK4083 dose level versus placebo) will be performed using an ANCOVA model with changes from Baseline in UCEIS, total Mayo Clinic score and partial Mayo Clinic score at Week 52 during Double-Blind Therapy Period as dependent variables, treatment as fixed effect and baseline value as covariate. The number of subjects and the number of subjects considered in the model will be provided by treatment. The adjusted means for treatments (least squares means) and the relative 95% CIs will be presented. The difference between the adjusted means for each treatment groups from placebo (Difference in Least Squares Mean from Placebo) will be calculated with the relative 95% CI and p-value. If ANCOVA cannot be applied

	Forms			
	Title	Statistical Analysis Plan Template		
	Code	Version	Effective Date	Page
	FRM_ST03_032	01	23 Apr 2015	33 of 53

due to the issue that the parameters cannot be estimated appropriately, these analyses using ANCOVA for Week 52 will not be applied.

Means with SDs for the efficacy variables (mMES, UCEIS, total Mayo score and partial Mayo score) at all visits will be performed graphically by each treatment (e.g. Placebo, 1.0 mg/kg, 3.0 mg/kg, or 10 mg/kg) and by Double-Blind Therapy Period and OLE Therapy Period. For partial Mayo score, Means with SDs as all visits will be performed graphically by “Double-Blind Therapy Period and Double-Blind Therapy Follow-up Period” and “OLE Therapy Period and OLE Therapy Follow-up Period”. Mean changes from Baseline will also be performed in the same manner.

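### SAP 7.3 scores change in steroid dosage as a 253- or 337-day count of administrations minus an on-treatment 112-day count, so this exploratory endpoint does not measure lowered dosage

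*SAP*

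**What the plan says.** The protocol lists lowered steroid dosage among its exploratory endpoints (Section 10.3) and plans to summarise change from Baseline from Week 16 onward (Section 12.3.3). It also fixes the reference point: "For efficacy assessments, Baseline is defined as Week 0" (Section 12.1). SAP Section 4.1 gives the same kind of general rule: "The baseline value for any measurement is the last value obtained prior to receiving administration of KHK4083 or placebo".

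SAP Section 7.3 departs from both. Its baseline steroid dosage is a count, worded as "administrations of glucocorticoid listed in Section 9.3 that is used during Double-Blind Induction Period (from Day 1 to a day before Week 16". The change to Week 52 is "Glucocorticoid dosages at Week 16 through Week 52 - Baseline glucocorticoid dosages". The OLE version that runs on to Follow-up 3 is "Glucocorticoid dosages at Week 16 through OLE Therapy Follow-up Period - Baseline glucocorticoid dosages", with a matching LTE version. The unit is a number of times, not mg. When that number is unknown, "it will be assumed that the glucocorticoid was used at a frequency of an administration per day".

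SAP Section 9.3 defines which steroids count: concomitant medications in ATC class H02AB that began to be given from Day 1. SAP Section 5.5, by contrast, treats a medication as concomitant whenever it started, provided it was taken during the study.

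**The concern.** Four features of the definition work against the endpoint.

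- The baseline is measured on treatment, against Protocol 12.1 and SAP 4.1. SAP 4.5, on changes to the planned analysis, does not record this as a departure.
- The window is labelled Induction, but the SAP's own design table reads "Induction Therapy: Week 0 to Week 12 (Last Dose at Week 10". During Screening and Induction, "subjects are not permitted to receive rescue therapy for UC including increases in corticosteroids or other medications for UC treatment", subject to the exceptions in Protocol 8.5. After Week 12, rescue, taper and dose adjustment become possible. The stretch from Week 12 to Week 16 therefore puts post-Induction steroid changes into the baseline.
- Raw counts over windows of unequal length are subtracted.
- A count of administrations cannot register a smaller dose taken equally often, and Protocol 8.1.4.2 and 8.5 express the taper in mg/day.

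At stake are Tables 14.2-3.5.1 and 14.2-3.5.2, whose values would not show whether dosage fell. Under one reading of SAP 9.3, classification of glucocorticoid-free remission at Week 52 is also affected.

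**Working it through.** The documents give no figure for these windows, so there is none to reproduce. The inputs are the SAP 7.3 window limits, the visit weeks and ±7-day visit windows in Protocol Table 9-2, and the dosing days in Protocol 8.1.4.1 (Days 1, 15, 29, 43, 57 and 71 for Weeks 0 to 10). Those days fit Day = 7 × week + 1, so Week 12 is Day 85, Week 16 is Day 113, Week 52 is Day 365 and Week 64 is Day 449.

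**Window lengths, both ends included**

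- Baseline, Day 1 to 112: 112 days, of which Day 85 to 112 (28 days, 25%) follow Week 12.
- Week 16 to Week 52: 365 − 113 + 1 = 253 days, or 253/112 = 2.26 times the baseline window.
- Week 16 to Follow-up 3: 449 − 113 + 1 = 337 days, or 337/112 = 3.01 times.

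**Unchanged once-daily background steroid, if counted**

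- To Week 52: 253 − 112 = +141. To Week 64: 337 − 112 = +225. The true change is 0.
- With visit days d16 and d52, the score is (d52 − d16 + 1) − (d16 − 1) = d52 − 2 × d16 + 2. For d16 from 106 to 120 and d52 from 358 to 372, it runs from 358 − 240 + 2 = +120 to 372 − 212 + 2 = +162. For Week 64 (Day 442 to 456) it runs from +204 to +246.
- A once-daily user who stops completely after Day 224 has 112 administrations in each window and scores 0.

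**Patterns compared to Week 52.** The taper example starts at 20 mg/day and falls by 2.5 mg/day each week, with the first step at Week 12. It reaches 2.5 mg at Week 18 and, if completed, 0 from Week 19 (Day 134), leaving 21 doses from Day 113 to Day 133. All use is once daily.

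| Pattern | True change, mg/day | Score if background counted | Score if 9.3 read literally |
|---|---|---|---|
| 20 mg/day throughout | 0 | 253 − 112 = +141 | 0 |
| Tapered to 2.5 mg and held | −17.5 | 253 − 112 = +141 | 0 |
| Tapered to zero | −20 | 21 − 112 = −91 | 0 |
| No background, rescue Day 92–98 (Week 13) | 0 | 0 − 7 = −7 | −7 |
| No background, rescue Day 141–147 (Week 20) | 0 | 7 − 0 = +7 | +7 |

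The zeros in the literal column arise because permitted background steroid must be stable before Screening (Protocol 8.5), so it started before Day 1. They would change only if a dose step opened a new medication record, which the documents do not say. The rescue rows assume a systemic product within the listed ATC class.

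**Glucocorticoid-free remission.** SAP 7.3 requires remission at Week 52 with no listed steroid used from Week 16 to Week 52. Under the literal reading, background steroid is not listed, so a remitter still taking it counts as glucocorticoid-free.

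**The case against.** The endpoint is one of many exploratory ones. SAP 4.1 disclaims hypothesis testing. The Week 52 models in SAP 7.3 cover UCEIS, total Mayo and partial Mayo, while steroid change is only summarised. No steroid table is among the unblinded Week 12 outputs in SAP 9.4.1. Individual data remain visible in Listings 16.2.5-1 and 16.2.6-3.2. The Week 16 start of the later window is the protocol's own choice (Sections 5, 10.3 and 12.3.3). The +141 and +225 figures also depend on the less literal reading of SAP 9.3. All of this stands. It limits the reach of the problem without making the subtraction meaningful.

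A reader might infer more than the documents support:

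- *That the inflated scores and the misclassified remissions occur together.* They arise under opposite readings of SAP 9.3 and do not add.
- *That the steroid-free duration has no end date for a subject with no later use.* SAP 7.3 defines that duration from Week 16 through Follow-up 3, which supplies one.
- *That early leavers would look steroid-sparing.* The SAP does not say where counting stops for them. Discontinued subjects have an End-of-Treatment visit and later follow-up (Protocol 7.5.4), with concomitant medication recorded at those visits (Table 9-2). No score can be assigned to them.
- *That one arm is favoured.* The documents do not say how many subjects use steroids, or in which arm.

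**Conclusion.** The definition is wrong as written, at a level between minor and should-fix, and for exploratory steroid endpoints only. It conflicts with the baseline rules in Protocol 12.1 and SAP 4.1, and under neither reading of SAP 9.3 does it measure lowered dosage. With background steroid counted, no change and a taper from 20 to 2.5 mg/day both score +141 at Week 52. With it omitted, held, tapered and stopped background use all score 0, and continuing users in remission count as glucocorticoid-free. The reversal of sign for a rescue course (−7 or +7) holds under both.

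These are single-subject illustrations on nominal visit days. They assume one administration per day, which is also the SAP default when the number is unknown. Neither an effect at arm level nor the number of misclassified remissions can be derived. The primary mMES analysis and the other Week 12 analyses are not affected.

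**What to change.** **SAP 7.3**

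- Define Baseline as the prednisolone-equivalent mg/day in use immediately before the first dose on Day 1, and 0 if none is in use then. It should not be the last record before dosing: UC medication is collected from 6 months before Screening (Protocol 8.5), so that record could be a course that ended long before.
- Define the later value as average mg/day in each window (Week 16 to Week 52; Week 16 to Follow-up 3): total mg divided by the subject's days on study in that window. Averaging captures rescue courses of up to 7 days that fall between four-weekly visits.
- Define change as that average minus Baseline, and delete the Day 1 to Week 16 baseline window.

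For the background patterns above, this gives 20 − 20 = 0 for unchanged use. The held taper gives (7 × 7.5 + 7 × 5 + 239 × 2.5)/253 − 20 = 685/253 − 20 = −17.3. The full taper gives 7 × (7.5 + 5 + 2.5)/253 − 20 = 105/253 − 20 = −19.6. A Week 13 rescue course falls before both windows and contributes 0; it would be seen only in the listings.

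If mg is not captured, use administrations per day on study with the same pre-dose Baseline. State that this cannot detect a dose reduction at unchanged frequency.

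**SAP 9.3.** Replace the restriction on start date with use on any day of the analysis window, whatever the start date. Apply the same list to glucocorticoid-free remission and duration.

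**Cost.** SAP wording, reprogramming of the derived variables, and conversion of concomitant-medication records to prednisolone equivalents. The sponsor must confirm whether mg is recorded and whether a dose step opens a new record. If the change is made after the Week 12 unblinding described in SAP 4.5, record it as such.

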12.6 Procedures for Missing, Unused, and Spurious Data

Missing values will not be substituted by estimated values, but treated as missing in the statistical evaluation. All data from all subjects dosed in the study will be included in all listings, plots, summary tables, and statistical analyses when appropriate.

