2.3 Exploratory objectives

- To determine if multiple doses of KHK4083 administered during Open-label Extension (OLE) or Long-term Extension (LTE) Therapy will meet the following objectives at Week 52 (or as noted) when compared with Baseline (Week 0) scores (or subscores) or assessments:
 - Improve clinical signs and symptoms based on total Mayo Clinic score;
 - Improve clinical signs and symptoms based on partial Mayo Clinic scores (excludes endoscopy subscores) at Week 16 through Week 52, and the OLE/LTE Therapy Follow-up Period (Week 56 through Week 64);
 - Induce a clinical response based on a reduction in the total Mayo Clinic score and rectal bleeding subscale (or a defined absolute rectal bleeding score);
 - Induce clinical remission based on a total Mayo Clinic score and subscores;
 - Induce durable clinical responses and durable clinical remissions (present at both Weeks 12 and 52), and glucocorticoid-free clinical remission;
 - Induce mucosal healing based on the mMES;

	Forms			
	Title	Statistical Analysis Plan Template		
	Code	Version	Effective Date	Page
	FRM_ST03_032	01	23 Apr 2015	10 of 53

- Improve the mucosa based on the mMES, UCEIS, and/or modified Baron endoscopic score;
 - Induce a remission (Week 12; Week 52) based on modified Mayo endoscopy, stool frequency, and rectal bleeding subscores (defined as an mMES of 0 or 1, stool frequency subscore of 0 or 1, and rectal bleeding subscore of 0).
- To evaluate the activity of KHK4083 on health-related quality of life (HRQL), which will be based on the subject's completed Inflammatory Bowel Disease Questionnaires (IBDQs) in comparison to Baseline assessments;
 - To measure changes from Baseline in corticosteroid (glucocorticoid) dosages;
 - To determine the percentage of subjects who are glucocorticoid-free from Week 16 through Week 52, and through the OLE/LTE Therapy Follow-up Period (Week 56 through Week 64);
 - To evaluate the pharmacodynamic (PD) profile of KHK4083;
 - To explore the PK-PD relationships.

3. Study Design

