4.4 Handling of missing and incomplete data

Available data at each time point will be presented. The denominator for percentages will be based on the number of subjects in the appropriate treatment or cohort group for summary purposes.

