Title Statistical Analysis Plan Template

Code

Version

Effective Date

Page

FRM_ST03_032

01

23 Apr 2015

42 of 53

Number	Title
Table 14.2-3.4.9	Summary Score and Change from Baseline in IBDQ - Emotional Status Score During Long-Term Extension Therapy Period and Double-Blind Therapy Follow-Up Period / Full Analysis Set
Table 14.2-3.4.10	Summary Score and Change from Baseline in IBDQ - Emotional Status Score During Open-Label Extension Therapy Period and Open-Label Extension Therapy Follow-Up Period / Full Analysis Set
Table 14.2-3.5.1	Summary Score and Change from Baseline in Corticosteroid (Glucocorticoid) Dosages During Long-Term Extension Therapy Period and Double-Blind Therapy Follow-Up Period / Full Analysis Set
Table 14.2-3.5.2	Summary Score and Change from Baseline in Corticosteroid (Glucocorticoid) Dosages During Open-Label Extension Therapy Period and Open-Label Extension Therapy Follow-Up Period / Full Analysis Set
Table 14.2-3.5.3	Summary Score and Change from Baseline in Duration of Corticosteroid-Free Treatment During Long-Term Extension Therapy Period and Double-Blind Therapy Follow-Up Period / Full Analysis Set
Table 14.2-3.5.4	Summary Score and Change from Baseline in Duration of Corticosteroid-Free Treatment During Open-Label Extension Therapy Period and Open-Label Extension Therapy Follow-Up Period / Full Analysis Set
Table 14.2-3.6	Percentage of Clinical Response at Week 52 During Double-Blind Therapy Period / Full Analysis Set
Table 14.2-3.7	Percentage of Clinical Response at Week 52 During Open-Label Extension Therapy Period / Full Analysis Set
Table 14.2-3.8.1	Change from Baseline in UCEIS at Week 52 During Double-Blind Therapy Period / Full Analysis Set
Table 14.2-3.8.2	Change from Baseline in Total Mayo Clinic Score at Week 52 During Double-Blind Therapy Period / Full Analysis Set
Table 14.2-3.8.3	Change from Baseline in Total Partial Clinic Score at Week 52 During Double-Blind Therapy Period / Full Analysis Set
Table 14.2-3.8.4	Mean Change from Baseline in Partial Mayo Clinic Scores During Double-Blind Therapy Period and Double-Blind Therapy Follow-Up Period / Mixed Model for Repeated Measures / Full Analysis Set
Table 14.2-3.9.1	Summary of Score and Change from Baseline in Mayo Clinic Score - Stool Frequency During Double-Blind Therapy Period and Double-Blind Therapy Follow-Up Period / Full Analysis Set

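### The SAP formula for glucocorticoid-free duration gives no value to subjects without a qualifying steroid after Week 16, so its summary covers only subjects who took one

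*SAP*

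**What the plan says.** SAP 7.3 first describes the endpoint in words, as "the duration that no glucocorticoid listed in Section 9.3 is used from Week 16 through Follow-up 3". It then gives the calculation: "Duration of glucocorticoid-free treatment (days) = Date of first glucocorticoid after Week 16 visit - Date of Week 16 visit". One special case follows: "If the subject received glucocorticoid on the date of Week 16 visit, the duration of glucocorticoid-free treatment for the subject is 0". No rule covers a subject with no glucocorticoid at all, and none covers a subject who leaves before Follow-up 3.

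For the neighbouring dosage variable, the same section does provide for non-users: "For the subject who receives no glucocorticoid, the dosages will be 0".

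The general rules do not fill the gap. SAP 4.4 says "Available data at each time point will be presented", and Protocol 12.6 says "Missing values will not be substituted by estimated values, but treated as missing in the statistical evaluation". SAP 4.1 summarises continuous variables over observed values.

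SAP 9.3 limits what counts as a glucocorticoid to concomitant medications in one ATC class (H02AB) whose administration began from Day 1. Protocol 8.5 allows stable oral glucocorticoids begun before Screening to continue.

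The related objective in SAP 2.3 is "To determine the percentage of subjects who are glucocorticoid-free from Week 16 through Week 52", and on through the extension follow-up. The tables planned for the duration (14.2-3.5.3 for the LTE and 14.2-3.5.4 for the OLE) carry titles of the form "Summary Score and Change from Baseline in Duration of Corticosteroid-Free Treatment During Open-Label Extension Therapy Period".

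**The concern.** The quantity is a time to first steroid, and for some subjects that event never happens. A formula that needs the event date can be evaluated only in subjects who had the event. The mean then describes how long steroid takers waited. It carries no information on how many subjects needed no steroid, which is what the objective asks. A dose group in which few subjects take a steroid, but those few take it early, would look worse than a group in which most take one later.

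Two further gaps sit beside this. The tables ask for a change from baseline in a duration that starts at Week 16 and has no baseline value; SAP 7.3 defines such a change only for dosages. And no table in SAP 9.4 is listed for the percentage of subjects who are glucocorticoid-free.

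**Working it through.** The documents state no figure for this variable, so there is nothing to reproduce. The check has three steps.

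**1. Apply the rules to each type of subject.**

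| Subject after Week 16 | Value under SAP 7.3 and 9.3 |
|---|---|
| Starts a qualifying steroid later | Difference of the two dates |
| Qualifying steroid on the Week 16 date | 0 |
| No steroid, reaches Follow-up 3 | None from the formula; the verbal definition suggests the whole window |
| No steroid, withdraws before Follow-up 3 | None from the formula; the verbal definition gives no end date |
| Continues unchanged a steroid begun before Day 1, starts no other | None, because SAP 9.3 does not count that steroid |

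The third and fifth rows are opposite outcomes, yet both end up without a value.

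**2. Can the ranking reverse?** For extension subjects Follow-up 3 is Week 64, so the nominal window is (64 − 16) × 7 = 336 days. Take two hypothetical groups of 10 with full follow-up.

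- Group A: 8 with no steroid, 2 users at 28 and 56 days. Formula mean (28 + 56)/2 = 42 days on n = 2. With non-users at 336: (8 × 336 + 84)/10 = 277.2 days on n = 10.
- Group B: 2 with no steroid, 8 users at 28, 56, …, 224 days (sum 1008). Formula mean 1008/8 = 126 days on n = 8. With non-users at 336: (2 × 336 + 1008)/10 = 168 days on n = 10.

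Group A uses fewer steroids, looks worse under the formula, and looks better once everyone counts.

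**3. How far apart can the two summaries be?** Assume a constant hazard, full follow-up to T = 336 days, and a share p who start a steroid. Then λ = −ln(1 − p)/T. The restricted mean over all subjects is R = p/λ. The users-only mean is U = (R − T(1 − p))/p.

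For p = 0.3: λ = 0.35667/336 = 0.0010615; R = 0.3/0.0010615 = 282.6; U = (282.6 − 235.2)/0.3 = 158.0.

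| Share starting a steroid | Users-only mean (days) | Mean over all subjects (days) | Gap (days) |
|---|---|---|---|
| 10% | 165.1 | 318.9 | 154 |
| 30% | 158.0 | 282.6 | 125 |
| 50% | 148.7 | 242.4 | 94 |
| 70% | 135.1 | 195.4 | 60 |

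When the share starting a steroid falls from 50% to 10%, the users-only mean rises by about 16 days and the all-subject mean by about 77. The share of subjects who contribute any value falls from 50% to 10%.

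**The case against.** The strongest reply is that the verbal definition governs. It names an end point, Follow-up 3, so a subject with no steroid plainly has the whole window, and the formula is only the working rule for subjects with a steroid date. On that reading nobody is excluded by design. This stands as evidence of intent, and it rules out saying that the SAP chose to exclude non-users. It does not supply a value: a programmer following the formula gets none, the neighbouring dosage variable shows that an explicit rule was written where one was wanted, and early withdrawals stay undefined on either reading.

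Second, an exclusion would be visible. SAP 4.1 reports n and counts of missing results, and Listing 16.2.6-3.2 shows each subject's dosages and duration. That is true and limits the harm, but a visible n does not make the users-only mean answer the question.

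Third, the objective is not wholly neglected. Dosages from Week 16 through Week 52 are set to 0 for non-users, so a percentage could be derived, and glucocorticoid-free clinical remission uses the same no-steroid condition. The first is fair, although SAP 9.3 would also give a 0 to continuing pre-study users. The second is a different, composite endpoint. Neither is a listed table of the percentage.

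Fourth, this is one exploratory, descriptive endpoint, absent from the Week 12 table list in SAP 9.4.1. That stands in full. Table shells are in a separate document and may refine the titles.

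**Conclusion.** The formula does not implement its own verbal definition. Followed literally, it summarises only subjects who took a qualifying steroid, leaves withdrawals without a rule, and can rank the group with less steroid use as worse. That is more than missing detail, because the written rule can give a wrong answer.

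Two stronger readings are tempting and should not be drawn:

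- A reader might infer that the subjects who drop out are simply the best outcomes. The documents do not support that. Under SAP 9.3 the group without a value also contains subjects who continue a steroid begun before the study.
- A reader might infer that steroid-free time will be understated by 94 to 154 days. Those gaps rest on assumed shares of 10% to 50% starting a steroid, a constant hazard, complete 336-day follow-up, and the literal reading of the formula. The documents give no steroid-use rate.

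The primary endpoint, the Week 12 analyses and the sample size are unaffected. The point is worth correcting before the extension tables are produced.

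**What to change.** 1. For this endpoint, count any systemic glucocorticoid taken on or after the Week 16 visit, including one started before Day 1, with duration 0 if it is ongoing at Week 16. This must come first. Censoring under the present SAP 9.3 would count continuing pre-study users as steroid-free.
2. Treat subjects with none as censored at Follow-up 3 or last contact.
3. Report n (%) glucocorticoid-free from Week 16 through Week 52 and through Follow-up 3, stating the denominator and how withdrawals are counted. Replace the users-only mean with a Kaplan-Meier estimate or a restricted mean. With groups this small the n (%) is the essential part.
4. Remove change from baseline from the titles of Tables 14.2-3.5.3 and 14.2-3.5.4.

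The cost is SAP wording and minor programming. Visit dates and concomitant medications, including those begun before the study, are already collected, so no new data and no change to trial conduct are needed.
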